### 3.3 Study procedures

After oral study information by [name], after signing the written study information and declaration of consent and clarifying the inclusion and exclusion criteria (health questionnaire), the measurement points are planned. A total of 6 measurement points are determined. The first 5 appointments take place once a month, followed by a 3-month measurement-free period, after which the last and 6th measurement takes place. In the event of complications or worsening symptoms, the head of the study, who is also the attending physician, is informed immediately.

If a conservatively treated patient needs surgery during the study (e.g. due to a worsening of his symptoms), the preoperative data set will be recorded and a new postoperative data set will be opened, provided that the patient wishes to continue participating and/or is not excluded by the study management. The study includes conservatively treated (physiotherapy) and surgically treated patients equally.

If imaging techniques are used in the context of medical diagnosis, these images are included in the data collection and taken into account as far as possible in the interpretation of the data.

**Overview of the procedure for recruiting subjects (by [name])**

Expiration	Screening	Overhead
- Medical diagnosis / clarification	Medical history, findings, diagnostic imaging	10 min
- Oral study information		
- Return of the signed study information and declaration of consent	Examination of inclusion and exclusion criteria	10 min
- Filling out the health questionnaire	Examination of inclusion and exclusion criteria	5 min

**Planning of measurement dates**

During the first measurement, the test person is instructed and given to keep the activity diary with a protocol for taking painkillers.

**Overview of the measurement process**

Expiration	Data collection	Instrument	Time exposure
- Questionnaire	subjective health-related quality of life	SF-36 Questionnaire	5 min
- Questionnaire	subjective physical impairment	ODQ	5 min
- Pain Evaluation	subjective pain radiation and intensity	VAS	5 min
- Demography	Height, body weight, body fat percentage	Pain Drawings Stadiometer, Tanita – Scale	5 min
- Ultrasound measurement of the rectus femoris and gastrocnemius medialis muscles	Thickness of subcutaneous fatty tissue, alignment of muscle fibers, bilateral	Portable Ultrasound Machine (TeleMed)	10 min
- Trunk mobility	Mobility of the spine in flexion, extension, lateral flexion	Sway Star™	2 min
- Hull swaying	Torso movements during 30 s – one-leg stand, both sides	Sway Star™	2 min
- Hull swaying	Trunk Movement during 8m - Walking	Sway Star™	5 min
- Neurodynamics	Pain provocation test, bilateral	Hydrogoniometer	2 min
- Evaluation of the sensor technology	Sensation of pressure, 2-point discrimination, sense of vibration, muscle reflex, pain threshold bilateral	Monofilament, Greulich Star, Neurological Tuning Fork, Reflex Hammer, Accelerometer, NOD Algometer	10 min
- Force measurement	maximum isometric force, force development, bilateral	NOD – isometric load cell, surface electromyography	5 min

The maximum time required per measurement appointment is one hour. With 6 measurement points, the time required adds up to 6 hours and extends over 8 months.

In addition, the patient keeps an activity diary at home and logs the painkiller intake, which takes about 5 minutes a day.

The treating physiotherapist records the content of all therapy sessions. The protocol to be used for this purpose is explained and instructed to the physiotherapist by the investigators at the beginning of the study. The documentation of physiotherapeutic treatment is one of the duties of a physiotherapist, so there is no additional effort for him. All he has to do is use the protocol template. Furthermore, the treating physiotherapists are asked to continue their usual interventions and treatments regardless of the study participation of their patients.

The following biases could occur:

- Sociodemographic and personal characteristics of the subjects: men/women, age
- Duration of back pain
- Truthful keeping of the activity diary and painkiller intake log
- physiotherapeutic treatment

By the time a patient presents to the neurosurgery department, the back pain has already reached a high degree of severity. The duration and intensity of symptoms vary and should be stratified in evaluation. The measurement times should be strictly adhered to in order to ensure comparability in time between the test subjects.

The study ends in the 8th month after the start of the study after the 6th and last measurement.

### **3.4 Withdrawal and discontinuation**

Participants will be excluded from the study if they do not (or cannot or do not want to) fulfill their obligations that entail participation in the study, or if they wish to voluntarily withdraw from participating in the study. Data that has already been collected is included in the data analysis as far as possible. If a conservatively treated patient needs surgery during the study (e.g. due to a worsening of his symptoms), the preoperative data set will be recorded and a new postoperative data set will be opened, provided that the patient wishes to continue participating and/or is not excluded by the study management.

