## **4 STATISTICS AND METHODOLOGY**

### **4.1. Statistical analysis plan**

The required number of subjects was determined a priori with G\*Power (version 3.1.9.2; Franz Faul University of Kiel, Germany). The following design specifications were used: statistical test = Correlation Type of Power Analysis 'Computer required sample size – given  $\alpha$ , power and effect size'; tails = two; effect size = 0.5;  $\alpha$  = 0.05; power = 0.95. The target number of subjects was  $n$  = 42 based on these design specifications. The SPSS version 24 software is used for statistical data analysis (IBM, Armonk, NY, USA).

The data are first checked for normal distribution with the 'Shapiro-Wilk test'. The normally distributed data are analysed by means of parametric test procedures. Non-normally distributed data as well as non-metric data are checked with non-parametric tests. The correlations are recorded using the 'Pearson Correlation tests' and 'Spearman Correlation tests'.

Correlations between the subjective parameters (pain, physical impairment, activity diary), between the objective parameters (strength, balance, sensory, neurodynamics, muscle thickness

and physiotherapeutic objectives), as well as between the subjective and objective parameters are of interest and should be calculated.

The following working (H1) and null hypotheses (H0) are statistically proven or rejected:

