## 4.2. Handling of missing data

Since statistical values of the individual relationships are determined, the data is also included if a test subject does not participate in all measurement points and/or measurements. Incomplete data from individual assessments (aborted tests) are not included in the final data analysis, but are recorded and stored.

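### Section 3.4 ends participation for anyone who does not or cannot meet unlisted obligations, so later visits are lost that most of the hypotheses could still use

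*Combined protocol and SAP*

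**What the plan says.** Section 3.4 (Withdrawal and discontinuation): "Participants will be excluded from the study if they do not (or cannot or do not want to) fulfill their obligations". The wording is mandatory, inability is named alongside unwillingness, and there is neither a list of obligations nor a threshold. The section then limits the consequence for the analysis: "Data that has already been collected is included in the data analysis as far as possible".

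Section 4.2 (Handling of missing data) takes an item-by-item approach: "the data is also included if a test subject does not participate in all measurement points and/or measurements". Aborted tests are handled in the same way: "Incomplete data from individual assessments (aborted tests) are not included in the final data analysis".

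The clearest continuing obligation is in section 3.3, under the measurement process: "the patient keeps an activity diary at home and logs the painkiller intake". This is put at about 5 minutes a day in a study with 6 measurement points over 8 months. Willingness to keep the diary is an entry criterion in section 3.1.

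Section 4.1 sizes the study for a two-sided correlation test with "effect size = 0.5", alpha and power given as "0.05; power = 0.95", and a target of "42 based on these design specifications". No allowance for exclusions or dropout is stated.

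**The concern.** Ending participation is a heavy response to failing one item. Someone who gives up the diary can still fill in the SF-36 and ODQ, rate pain, and undergo the force, sway and sensory tests. Someone who cannot do one physical test can usually do the others. Under a literal reading of section 3.4, all of these are forgone from that point on.

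Two things are at stake at the visits after an exclusion. The first is fewer observations, in a study whose background section says it wants to follow these parameters over time. The second is selection. Being unable to comply may go with more pain or impairment, which are themselves among the variables being correlated. If so, their range narrows at later visits and correlations shrink toward zero. The list of possible biases in section 3.3 does not mention this.

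There is also a practical ambiguity. Missing a visit could count as failing an obligation under 3.4, while 4.2 treats it as ordinary missing data. Two staff members could handle the same missed visit differently.

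**Working it through.** **1. How many hypotheses need the diary.** Section 4.1 lists 5 hypotheses under pain, 5 under physical impairment and quality of life, 4 under force and 3 under trunk mobility: 5 + 5 + 4 + 3 = 17. The activity diary appears in one of the pain hypotheses and one of the impairment hypotheses. That leaves 17 − 2 = 15 that need no diary data.

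**2. Which visits are affected.** The diary is handed out at the first measurement, so diary failure cannot affect visit 1. Because collected data are retained, the visits before an exclusion keep their n and their range. Only the visits after it are affected.

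**3. The plan's own sample size.** Inputs from section 4.1: r = 0.5, two-sided alpha 0.05, power 0.95. With the noncentral t model, df = N − 2 and noncentrality = √(N·r²/(1 − r²)). At N = 42 this is √(42 × 0.25/0.75) = √14 = 3.74 and power is 0.9545; at N = 41 power is 0.94995. So N = 42 reproduces. Under the exact bivariate-normal model, power at 42 is 0.935.

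**4. Worst case at a visit after exclusion.** Assumptions: true r = 0.50, bivariate normality, exactly the most impaired share q absent, and none of their data available at that visit.

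For truncation at c = Φ⁻¹(1 − q), the remaining variance is v = 1 − cφ(c)/(1 − q) − [φ(c)/(1 − q)]². With u = √v, the attenuated correlation is r = 0.5u/√(0.75 + 0.25u²).

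- q = 10%: u = 0.844, r = 0.438, n = 42 × 0.9 ≈ 38.
- q = 20%: u = 0.764, r = 0.403, n = 42 × 0.8 ≈ 34.

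Fisher-z power is approximately Φ(atanh(r)·√(n − 3) − 1.96).

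- q = 10%: 0.470 × √35 − 1.96 = 0.82, power 0.79. The exact bivariate model gives 0.80.
- q = 20%: 0.427 × √31 − 1.96 = 0.42, power 0.66. The exact model gives 0.68.
- Same numbers lost at random (r stays 0.50, atanh = 0.549): power 0.90 at n = 38 and 0.86 at n = 34.

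**5. Softer dependence.** Assumption: the log-odds of being excluded rise by 1 to 1.5 per SD of impairment, with the intercept set to give the same overall loss (simulation; Fisher-z power).

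| Share lost | n | r | Power | Power if lost at random |
|---|---|---|---|---|
| 10% | 38 | 0.48–0.49 | 0.87–0.88 | 0.90 |
| 20% | 34 | 0.46–0.48 | 0.80–0.83 | 0.86 |

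In this range the selective part of the loss costs about 2 to 7 points of power beyond the loss of n.

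**The case against.** A reader might infer that sections 3.4 and 4.2 contradict each other. They do not. Section 3.4 decides who continues; section 4.2 decides which data are analysed; and both keep partial data. What remains is a tension over whether a missed visit or measurement is missing data or a ground for exclusion.

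A reader might also infer that the rule removes the most impaired patients. The documents do not show this. They do not link failure to comply with impairment, and the rule also covers people who are simply unwilling, who could be recovered or busy. One clearly worsening group has its own route: a conservatively treated patient who needs surgery may continue with a new postoperative data set, subject to the patient's wish and the study management.

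That the diary is one of the obligations is itself a reading. Section 3.4 does not name it, and section 3.1 asks for willingness, not completeness. The reading is reasonable, because the diary is the main task asked of participants between visits, but it remains a reading.

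Finally, the truncation figures could be taken as the expected loss for the whole study. They are an upper illustration, since loss is unlikely to follow severity exactly and earlier visits are retained.

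These objections limit the size and certainty of the effect. They do not alter the fact that the stated rule is mandatory, includes inability, has no threshold and gives up later data that could still be collected.

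**Conclusion.** The point stands as a defect in a stated rule, of moderate to small and uncertain size. The certain part is that section 3.4, followed as written, can end all later measurements over a single unmet obligation, although 15 of 17 hypotheses do not use the diary and section 4.2 already handles missing items one at a time.

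The conditional part is attenuation at the visits after exclusion. It requires that inability be related to pain or impairment and that enough participants be excluded to matter. The documents give no exclusion rate, so the 10–20% shares, the true r of 0.50 and bivariate normality are all assumptions. On the softer assumption the correlation moves little. The larger drop, with power about 0.80 to 0.67, needs near-complete loss of the most impaired. The documents support neither a demonstrated bias nor a flat contradiction between the two sections.

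**What to change.** Reword section 3.4 so that, after enrolment, not completing the diary or an individual measurement does not by itself end participation. The affected item is set to missing and the remaining scheduled measurements continue, in line with section 4.2. In the same edit, state what the obligations are and what is meant by using collected data as far as possible.

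Leave three things as they are: voluntary withdrawal, diary willingness as an entry criterion, and the study management's discretion to exclude. The last appears in sections 3.3 and 3.4, and a rule that participation ends only at the participant's request would remove it.

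The change is short and adds no procedures. Its cost is somewhat more missing data in the two diary hypotheses, because participants with incomplete diaries stay in the study. Reporting the number excluded and the reasons, by visit, would let readers judge whether selection at later visits mattered.

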## **4 STATISTICS AND METHODOLOGY**

### **4.1. Statistical analysis plan**

The required number of subjects was determined a priori with G\*Power (version 3.1.9.2; Franz Faul University of Kiel, Germany). The following design specifications were used: statistical test = Correlation Type of Power Analysis 'Computer required sample size – given  $\alpha$ , power and effect size'; tails = two; effect size = 0.5;  $\alpha$  = 0.05; power = 0.95. The target number of subjects was  $n$  = 42 based on these design specifications. The SPSS version 24 software is used for statistical data analysis (IBM, Armonk, NY, USA).

The data are first checked for normal distribution with the 'Shapiro-Wilk test'. The normally distributed data are analysed by means of parametric test procedures. Non-normally distributed data as well as non-metric data are checked with non-parametric tests. The correlations are recorded using the 'Pearson Correlation tests' and 'Spearman Correlation tests'.

Correlations between the subjective parameters (pain, physical impairment, activity diary), between the objective parameters (strength, balance, sensory, neurodynamics, muscle thickness

and physiotherapeutic objectives), as well as between the subjective and objective parameters are of interest and should be calculated.

The following working (H1) and null hypotheses (H0) are statistically proven or rejected:

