#### Objectification power:

The hand-held dynamometer (NOD, [www.to-nod.com](http://www.to-nod.com)) graphically and numerically records the strength and duration of the isometric power delivery. Superficial electromyography is performed with the PLUX EMG device ([www.biosignalsplux.com](http://www.biosignalsplux.com)) and evaluated with the associated software.

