### - **Sensors**

The sensory system of the affected area (segmentally associated dermatome) is tested directly on the skin in the radiation area. The results are transferred to the data sheet. The pain threshold is raised on a Valleix point along the iliac crest. Measurements are always taken at the same measuring points, on the affected side.

Objectification of sensor technology:

The pressure sensation is recorded by means of a monofilament, the 2-point discrimination with the Greulich star, the sense of vibration with the tuning fork (according to Rydel-Seiffer), the muscle reflex with the reflex hammer in a left/right comparison including acceleration measurement (accelerometer MSR165, [www.msr.ch](http://www.msr.ch)) and the pain threshold with the algometer (NOD, [www.to-nod.com](http://www.to-nod.com)).

- **Neurodynamics**

The neurodynamics of the affected spinal nerve are tested using the appropriate pain provocation test. For this purpose, a hydrogoniometer is required, with which the exact number of degrees at which the symptoms are triggered is measured. The number of degrees is transferred to the data sheet. The tests are carried out in a standardised manner. If the spinal nerve L2/L3 is affected, the crossed Lasègue test is performed, and for L4/L5/S1 the Lasègue test.

Objectification of neurodynamics:

Hydrogoniometer

- **Subcutaneous fat tissue and muscle fiber alignment**

The thickness of the subcutaneous fatty tissue is measured on the rectus femoris muscle, 10 cm above the patellar base, and on the medial gastrocnemius muscle at the level of the largest calf circumference, in both legs.

Objectification Thickness Subcutaneous Fat Tissue and Muscle Fiber Alignment:

The portable ultrasound device from Telemed ([www.pcultrasound.com](http://www.pcultrasound.com)) is used for this purpose. The images are evaluated with the Osirix ([www.osirix-viewer.com](http://www.osirix-viewer.com)) software and the number of millimetres, fat thickness and muscle fibre degree angle are transferred to the data sheet.

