#### Force (isometric force measurements)

---

H0 There is no correlation between isometric force and trunk mobility and trunk fluctuations.  
H1 There is a correlation between isometric force and trunk mobility and trunk fluctuations.

H0 There is no correlation between isometric force and sensing.  
H1 There is a correlation between isometric force and sensing.

H0 There is no correlation between isometric force and thickness of the subcutaneous fat layer and muscle fiber alignment.  
H1 There is a correlation between isometric force and thickness of the subcutaneous fat layer and muscle fiber alignment.

H0 There is no correlation between isometric strength and physiotherapeutic objective.  
H1 There is a correlation between isometric strength and physiotherapeutic objectives.

---

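### The stated power of 0.95 at n = 42 matches an unnamed point-biserial/fixed-X model; for a Pearson correlation of two measured continuous variables, power at 42 is 0.935

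*Combined protocol and SAP*

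**What the plan says.** Section 4.1 (Statistical analysis plan) contains the study's only sample-size justification. It names G*Power 3.1.9.2 and gives these settings: "statistical test = Correlation Type of Power Analysis", "tails = two; effect size = 0.5", alpha 0.05, power 0.95. The target number of subjects is "42 based on these design specifications". As the text reads, the test is identified only as a correlation, with no model.

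The same section routes the analysis by distribution: "The normally distributed data are analysed by means of parametric test procedures", and "Non-normally distributed data as well as non-metric data are checked with non-parametric tests". Pearson and Spearman are the named correlation procedures.

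Some of the variables to be correlated are plainly continuous measurements. One null hypothesis under Force in section 4.1 reads: "There is no correlation between isometric force and thickness of the subcutaneous fat layer and muscle fiber alignment". Section 2.2 says that the dynamometer "graphically and numerically records the strength and duration of the isometric power delivery". For the ultrasound images, "the number of millimetres, fat thickness and muscle fibre degree angle are transferred to the data sheet".

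**The concern.** With the same four inputs (two-sided, 0.5, 0.05, 0.95), different correlation models give different sample sizes. A reader who enters them under the bivariate-normal model gets 46, not 42, and cannot tell from the text whether 42 is an error or comes from another model.

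The choice also affects what the 0.95 covers. The point-biserial/fixed-X model takes one variable as given, either a dichotomy or values set in advance. This is an observational study with no intervention (section 2.3), and force, fat thickness and fibre angle are all observed on patients, so none is fixed by design. When both variables vary at random, the sample spread of each varies too, and power at a given n is lower. If 42 came from the fixed-X model, the stated power is too high for pairs of this kind. Section 8 plans several articles from these data, so the same power statement could be repeated in each.

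**Working it through.** **Inputs** (all from section 4.1): ρ = 0.5 under the alternative, two-sided α = 0.05, target power 0.95, n = 42. Each patient is assumed to contribute one complete pair.

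**Step 1: reproduce 42.** Under the point-biserial/fixed-X model the test statistic is noncentral t with n − 2 degrees of freedom and noncentrality δ = √(n ρ²/(1 − ρ²)). With ρ = 0.5, ρ²/(1 − ρ²) = 0.25/0.75 = 1/3, so δ = √(n/3).

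- n = 41: δ = √13.667 = 3.697, 39 df, power 0.94995, just under target.
- n = 42: δ = √14 = 3.742, 40 df, critical t = 2.021, power 0.9545.

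The smallest n reaching 0.95 is therefore 42, an exact match.

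**Step 2: check whether another model also gives 42.**

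| Model | n for power 0.95 |
|---|---|
| Point-biserial/fixed-X, two-sided | 42 |
| Bivariate normal, exact, two-sided | 46 |
| Fisher z, two-sided: ((1.960 + 1.645)/0.5493)² + 3 = 46.07 | 47 |
| Fisher z with bias correction, two-sided | 46 |
| Bivariate normal, exact, one-sided | 38 |
| Point-biserial/fixed-X, one-sided | 34 |

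Of the variants tried, only the two-sided point-biserial/fixed-X model returns 42. That it was used is an inference from this match.

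**Step 3: power of the Pearson test when both variables are random.** The two-sided test rejects when |r| exceeds r_c = t_c/√(n − 2 + t_c²). At n = 42 this is 2.021/√(40 + 4.085) = 0.304. Power is the integral beyond ±r_c of the exact density of r under bivariate normality:

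f(r) = (n − 2) Γ(n − 1) (1 − ρ²)^((n−1)/2) (1 − r²)^((n−4)/2) / [√(2π) Γ(n − ½) (1 − ρr)^(n−3/2)] × ₂F₁(½, ½; (2n − 1)/2; (1 + ρr)/2)

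As a check, this density integrates to 1 at n = 42.

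| n | Point-biserial/fixed-X | Bivariate normal, exact |
|---|---|---|
| 41 | 0.94995 | 0.92895 |
| 42 | 0.95453 | 0.93467 |
| 43 | 0.95871 | 0.93995 |
| 44 | 0.96253 | 0.94484 |
| 45 | 0.96601 | 0.94935 |
| 46 | 0.96919 | 0.95351 |

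Simulation with 400,000 data sets agrees: 0.935 at n = 42 and 0.954 at n = 46.

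**Step 4: size of the gap.** Power falls short by 0.950 − 0.935 = 0.015. Type II error is 0.065 against the stated 0.05. Equivalently, 46 − 42 = 4 more complete pairs would be needed, or the true correlation would have to be about 0.516 for 42 pairs to give 0.95.

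**Step 5: limits of the point.** If one variable is dichotomous and observed at random (point-biserial correlation 0.5, normal within groups), simulated power at 42 is 0.950 for a 50/50 split, 0.943 for 30/70 and 0.929 for 20/80. The 0.95 therefore holds for a roughly even dichotomy. These splits are assumptions, since the documents define no dichotomous variable. For Spearman, simulation of bivariate-normal data with Pearson ρ = 0.5 gives about 0.90 at n = 42. A large-sample approximation with variance 1.06/(n − 3) and a rank correlation of 0.5 gives 0.915. These Spearman figures are only a guide, because data sent to Spearman will by rule be non-normal or non-metric.

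**The case against.** The strongest objection is materiality. The effect size is given to one decimal with no source, and 0.516, the value at which 42 pairs deliver 0.95, itself rounds to 0.5. The gap is thus no larger than the rounding of the input, and no design or analysis decision depends on it. That stands, and it is why the point is minor. It does not make 0.95 the right figure for the inputs as stated.

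Second, the sentence in section 4.1 visibly runs two G*Power fields together, so a model name may have been lost from the text. That cannot be excluded. A lost name would remove the reporting gap but would not change the power of a Pearson test on two continuous variables.

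Third, the affected set is uncertain. Which pairs reach Pearson depends on the Shapiro-Wilk results, and only force against fat thickness and fibre angle is worked through here. This is fair, and the conclusion is limited to continuous pairs analysed by Pearson. The alternative route offers no rescue, since the guide figures for Spearman are lower still.

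Fourth, one complete pair per patient is itself an idealisation. There are six measurement points (section 3.3) and bilateral measurements, and the plan does not say which time point or side enters a correlation. That is true, but a sample size for one correlation, which is what section 4.1 presents, rests on the same simplification.

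**Conclusion.** The concern holds, as a minor point. The figure 42 is correctly computed under the two-sided point-biserial/fixed-X model, but the text does not name that model and it does not describe a Pearson correlation between two continuous variables both measured on patients. For those pairs, power at 42 is 0.935 rather than 0.95, and 46 complete pairs would be needed.

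This rests on ρ = 0.5, two-sided α = 0.05, bivariate normality and one complete pair from each of 42 patients. The power values do not depend on which G*Power option was selected; only the explanation of where 42 came from is inferred. The conclusion does not extend to a pair with a roughly evenly split dichotomous variable. Multiplicity, attrition and the justification of 0.5 are separate questions and are not judged here.

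**What to change.** In section 4.1, name the G*Power correlation model that produced 42, and add a sentence along these lines:

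> With 42 patients contributing a complete pair, two-sided alpha 0.05 and rho = 0.5, power for a single Pearson correlation of two continuous variables is about 0.93 (exact bivariate-normal model; 46 would be needed for 0.95). Power for Spearman correlations on non-normal or ordinal data was not calculated and may be lower.

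The enrolment target, hypotheses and procedures stay as they are. The cost is one sentence and a slightly less favourable stated power. In return, a reader can reproduce 42 and see which pairs the 0.95 covers.

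### The stated power of 0.95 at n = 42 makes no allowance for the planned Spearman tests or for lost pairs; 42 complete pairs give about 0.93 with Pearson and about 0.90 with Spearman

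*Combined protocol and SAP*

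**What the plan says.** Section 4.1 contains the only power statement. It gives the G*Power entry as "statistical test = Correlation Type of Power Analysis", two tails, "effect size = 0.5", and alpha and power as "0.05; power = 0.95". It then states: "The target number of subjects was" 42. It does not name which of the G*Power correlation models was used.

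The same section sets the tests by a normality check. "The normally distributed data are analysed by means of parametric test procedures", whereas "Non-normally distributed data as well as non-metric data are checked with non-parametric tests". Both coefficients are planned: "The correlations are recorded using the 'Pearson Correlation tests' and 'Spearman Correlation tests".

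On incomplete data, section 4.2 says that "the data is also included if a test subject does not participate in all measurement points" or in all measurements, and it leaves aborted tests out of the final analysis. Section 3.4 provides for withdrawal and exclusion and keeps what was collected as far as possible. Section 3.3 sets six measurement points over 8 months. No section gives an expected loss rate, an inflation of 42, or a power for Spearman.

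**The concern.** The power of 0.95 applies to one parametric test on 42 complete pairs. Some of the planned analyses will not be of that kind. Section 2.2 measures sensation partly with a monofilament and a graded tuning fork, which are step scales and so point to the rank test. Sensory function enters 4 of the 17 hypothesis pairs in section 4.1. The pain scale, questionnaire totals and percentage pain area go the same way if the normality check fails. Any subject who misses or aborts one of two measurements contributes no pair to that correlation.

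The plan intends each null hypothesis to be either proven or rejected. A reader told that power is 0.95 would treat a non-significant result as good evidence against a correlation of 0.5, since the stated chance of missing one is only 5%. If the true chance is higher, that reading is too confident.

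**Working it through.** **Inputs.** From section 4.1: r = 0.5, two-sided alpha 0.05, power 0.95, n = 42. Assumed here: one pair per subject in each correlation (the plan does not say which of the six measurement points, or which summary, is used), and the loss rates below.

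**Step 1: reproduce 42.** Three models were tried with these inputs.

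- Point-biserial: noncentral t with n − 2 degrees of freedom and noncentrality √(n·r²/(1 − r²)). For n = 41 this is √(41 × 0.25/0.75) = 3.697, power 0.94995. For n = 42 it is √(42 × 0.25/0.75) = 3.742, power 0.9545. The smallest n reaching 0.95 is 42, so the plan's figure reproduces.
- Pearson, exact bivariate normal: n = 45 gives 0.9493 and n = 46 gives 0.9535, so 46 are needed. Power at 42 is 0.935.
- Fisher z: n = ((1.960 + 1.645)/atanh 0.5)² + 3 = 46.07, rounded up to 47. Power at 42 is 0.929.

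One-sided versions give 34 (point-biserial) and 38 (Pearson), so they do not explain 42 either.

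**Step 2: Spearman at 42 pairs.** Bivariate normal samples with r = 0.5 were simulated and ranked, and the rank correlation was compared with the critical value t/√(n − 2 + t²), where t is the 0.975 quantile on n − 2 degrees of freedom. For n = 42, t = 2.021 and the critical value is 0.304. With 200,000 samples, power is 0.90.

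This depends on what 0.5 refers to and on the shape of the data:

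- A bivariate normal r of 0.5 corresponds to a rank correlation of (6/π)·arcsin(0.25) = 0.483. If 0.5 is instead the rank correlation itself (normal r = 2·sin(π × 0.5/6) = 0.518), Spearman power at 42 is about 0.92.
- With one variable cut to five equal-probability ordered levels (an assumed scale), it is about 0.88. With both variables cut to five levels, it is about 0.865.
- For heavy-tailed data (bivariate t, 3 degrees of freedom), Spearman has about 0.85 and Pearson about 0.83.

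**Step 3: lost pairs.** A 10% loss leaves 42 × 0.90 = 37.8, about 38 pairs. A loss of 6 of 42 (14%) leaves 36, and 12 of 42 (29%) leaves 30.

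| Complete pairs | Loss (assumed) | Pearson | Spearman, bivariate normal |
|---|---|---|---|
| 42 | none | 0.93 | 0.90 |
| 38 | 10% | 0.91 | 0.87 |
| 36 | 14% | 0.89 | 0.85 |
| 30 | 29% | 0.83 | 0.77 |

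**Step 4: separate the causes at 42 pairs.** The stated type II error is 0.05. Pearson has 1 − 0.935 = 0.065 and Spearman 1 − 0.902 = 0.098. The move from 0.05 to 0.065 comes from the power model. The move from 0.065 to 0.098, a factor of 0.098/0.065 ≈ 1.5, is due to Spearman. For reference, power of 0.95 would need 46 complete pairs with Pearson and about 51 with Spearman.

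**The case against.** The strongest reply is that the shortfall is small and its size uncertain. Pearson at 42 pairs is within 2 points of 0.95. The 0.90 for Spearman is computed on bivariate normal data, which the plan would send to Pearson. For the variables that do go to Spearman, power depends on their shape, and with heavy tails the rank test does better than Pearson. The number of hypotheses affected is not fixed: only the step-scale sensory tests are clearly non-metric, and the sensory battery also includes an algometer and an accelerometer. Section 4.2 is a rule for handling gaps, not a forecast of them, and a missed later visit need not remove a pair from a baseline or averaged analysis. The study is observational and has no single primary hypothesis.

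Most of this stands, and it rules out three stronger readings that a reader might infer. The first is that 0.90 is the best the study can do. It is not: pairs kept on Pearson have about 0.93, and Spearman has about 0.92 if 0.5 is the rank correlation. The second is that using Spearman doubles the type II error. That would charge the model gap to the rank test, whose own effect is about 1.5 times. The third is that the trial will run at 0.77 to 0.85. Those values need 14% to 29% of pairs lost, a range that the documents do not give.

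The reply does not rescue the 0.95. Under the stated inputs, none of the Pearson or Spearman settings checked in the working reaches it at 42 pairs, and the plan permits losses without allowing for any.

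**Conclusion.** The point holds in limited form. The power of 0.95 at n = 42 is the output of a single parametric calculation that reproduces only under the point-biserial model. It makes no allowance for the Spearman tests that section 4.1 requires for non-normal and non-metric data, or for the losses that sections 3.4 and 4.2 permit.

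With complete data the overstatement is about 2 points for Pearson and 5 for Spearman on bivariate normal data. It becomes material only as pairs are lost, reaching 12 and 18 points at 30 pairs. These sizes rest on an underlying r of 0.5, one pair per subject and assumed loss rates.

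It would go too far to infer that 42 subjects are too few for the study to be useful. The documents do not support that: power stays at about 0.77 or more in the tabulated scenarios, and the defect lies in the power claim, not in the enrolment target.

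**What to change.** Keep 42 subjects. In section 4.1, name the G*Power model that gave 42 and replace the claim of 0.95 with a statement such as:

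> For an underlying correlation of 0.5, a two-sided level of 0.05 and one pair per subject, 42 complete pairs give power of about 0.93 with Pearson and about 0.90 with Spearman (bivariate normal data; about 0.92 if 0.5 is the rank correlation, about 0.88 if one variable has five ordered levels). With assumed losses of 10%, 14% and 29%, the remaining 38, 36 and 30 pairs give about 0.91, 0.89 and 0.83 with Pearson and 0.87, 0.85 and 0.77 with Spearman.

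Print the number of complete pairs beside every reported correlation, so that a non-significant result can be read against the power it had.

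The cost is a short passage in section 4.1 and one column in the results tables. No procedure, test or enrolment figure changes. The stated power becomes less favourable.
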